Study Protocol and Statistical Analysis

[figure not shown]
A. Study Protocol

1. Research subjects

The research subjects were patients with CHB receiving ETV or second-line NA (LAM/ADV/LdT) who were admitted to The Second Affiliated Hospital of Chongqing Medical University and other centers.

2. Research design

96-week multi-centre prospective real world study

3. Research methods

In our hospital, about 150 patients are screened for HBV-DNA every day. Therefore, 54 million patients will be tested for HBV-DNA within one year, of which 30% are estimated to be HBV-DNA ≥ 10 IU. These patients will be informed to the Department of Infectious Diseases of the Second Affiliated Hospital of Chongqing Medical University for follow-up, and will be randomly divided into three groups according to 1:1. Patients in all three groups will be educated about hepatitis B virus infection and antiviral treatment, and the treatment regimen will be adjusted according to whether their HBV DNA is ≥ 10 IU/ml or not. Patients in group 1: patients with persistent low level HBV DNA (< 10 IU/ml). Patients in group 2: HBV-DNA ≥ 10 IU/ml, receiving HBV-related education and being advised by the doctor to change or to add another NA. Patients in group 2: patients with persistent HBV DNA (> 10 IU/ml) but refuse to change the regimen. Patients in group 3: patients with persistent HBV DNA (> 10 IU/ml) and agree to change the regimen. Educational methods include videos, including an introduction to hepatitis B virus (disease profile, infection, outcome, HBV infection, vertical transmission and other risk factors) for 5 minutes, brochures with relevant information and consultations with physicians and nurses.

All patients with CHB receiving ETV or second-line NA (LAM/ADV/LdT) treatment for more than six months to one year will receive HBV-DNA

detection, and patients with HBV-DNA \geq 10 IU/ml will be informed and recommended to adjust the treatment regimen so that we could obtain the actual prevalence of HBV-DNA load $<$ 10 IU/ml in Chongqing HBV cohort. We estimated that 30% of the patients had HBV-DNA \geq 10 IU/ml, so there were about 16,200 patients had HBV-DNA \geq 10 IU/ml among 54,000 patients a year. These patients will be diagnosed with LLV and will undergo a treatment regimen adjustment, with a recommendation to switch to or use a different type of NA for viral treatment.

4. Outcome indexes

(i) The main index:

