The proportion of patients who received a complete virologic response (HBV DNA $<$ 10 IU/ml) at 24 weeks after therapy adjustment.

(ii) The secondary index:

1. The proportion of patients with complete virologic response (HBV DNA $<$ 10 IU/ml) at 12 weeks, 48 weeks and 96 weeks after therapy adjustment.

2. The proportion of patients with normal ALT at baseline and at each follow-up time point.

3. Changes of bone and kidney indicators (eGFR, SCr, BMD, etc.) compared with baseline at each follow-up time point.

B. Statistical Analysis

1. Statistical description

. Whether the measurement data conforms to normal distribution: the statistical method is modified or the data is converted when the measurement data does not conform to normal distribution, then it is managed as normal distribution when the mean and median are close due to the large sample size because of the opening test. Outliers: Statistical and professional analysis is performed to determine whether to keep outliers. Management of missing value in major efficacy indicators data: when a major efficacy data is missing in individual subjects, the method of filling is determined from a statistical and professional perspective. If the case is lost, data from the previous measurement shall be transferred.

. Case analysis of unfinished tests: the reason of lost cases should be analyzed one by one.

. Descriptive statistics: indicating the mean, the standard deviation, the maximum, the minimum, the median, the upper and lower quartile (Q1 and Q3), the confidence interval, the frequency (composition ratio), etc.

2. Statistical inference method

. The measurement data: T test, paired T test, rank sum test, paired

rank sum test, correlation analysis was used. The counting data: Chi-square test, Fisher exact test, etc. The grade data were tested by CMH method.

3. Statistical expression

- . The report is mainly expressed in tables, which are self-explanatory, that is, with headings, notes and main statistical indicators.
- . The results of repeated measurements are presented in tables with statistical charts for readability. F value and P value of an OVA of repeated measurement data are added.
- . Bilateral tests are generally used for statistical tests, and P less than or equal to 0.05 is considered to be statistically significant.

4. Statistical software

SPSS22.0 software will be used for analysis.

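### The binary main index is compared by tests that ignore centre, although the study is multi-centre and groups 2 and 3 are self-selected, so centre can confound the contrast

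*Combined protocol and SAP*

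**What the plan says.** Section A.2 calls this a "96-week multi-centre prospective real world study". Section A.1 takes patients "who were admitted to The Second Affiliated Hospital of Chongqing Medical University and other centers". Neither the number of centres nor their expected sizes is given.

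Section A.3 first says that patients "will be randomly divided into three groups according to 1:1". It then describes group 2 twice, the second time as "patients with persistent HBV DNA (> 10 IU/ml) but refuse to change the regimen", and group 3 as "patients with persistent HBV DNA (> 10 IU/ml) and agree to change the regimen". On these definitions the patient's decision, not an allocation list, places a patient in group 2 or group 3.

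The main index in A.4 is a proportion: complete virologic response at 24 weeks. The secondary indexes are further proportions (response at other weeks, normal ALT) and changes in eGFR, SCr and BMD.

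For analysis, B.2 states: "The counting data: Chi-square test, Fisher exact test, etc. The grade data were tested by CMH method". Measurement data go to t, rank-sum, paired and correlation methods, and B.3 adds a repeated-measures ANOVA. Centre does not appear in any of these as a stratum, covariate, random effect or cluster. CMH is the one listed method that can stratify. Its stratum is not named, it is kept for graded data, and none of the listed indexes is graded.

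**The concern.** Centre biases a comparison of groups 2 and 3 only when it is related both to group and to outcome.

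The first link is plausible because group membership follows a patient's decision after education and consultation with physicians and nurses, and uptake of advice may differ between sites. The second is plausible because the study mixes patients on ETV with patients on LAM, ADV or LdT, and that mix may differ between sites. The documents establish neither link, and they plan nothing that would protect the comparison if both exist.

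What is at stake is the main comparison. A centre with both high agreement and high response would give group 3 an apparent advantage with no effect of changing regimen, and a pooled chi-square test cannot tell the two apart.

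**Working it through.** The documents state no sample size, effect size, response rate, number of centres or between-centre variation, so there is no stated figure to reproduce. Every input below is an assumption. The plan does not spell out which groups are compared; the contrast taken here is group 3 against group 2.

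**1. Two-centre arithmetic.** Take two equal centres, A and B, with 200 patients per group, 50% mean response, 50% mean agreement and no true effect. Let p be the response rate and s the share agreeing at each centre.

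- Group 3 response = (sA·pA + sB·pB) / (sA + sB)
- Group 2 response = [(1−sA)·pA + (1−sB)·pB] / (2 − sA − sB)

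With pA = sA = 0.6 and pB = sB = 0.4:

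- Group 3: (0.36 + 0.16) / 1 = 0.52
- Group 2: (0.24 + 0.24) / 1 = 0.48
- Spurious difference: 4 points

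With both averages at 50%, the bias is the product of the two gaps: 0.2 × 0.2 = 0.04.

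The SE used by the pooled comparison is √(2 × 0.52 × 0.48 / 200) = 0.0500. The SE given the centre mix is √(2 × 0.24 / 200) = 0.0490. The two-sided 5% test then rejects 12.1% of the time. The same steps give, as bias / false-positive rate:

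| Response gap between centres | Agreement gap 0 | Agreement gap 20 points | Agreement gap 40 points |
|---|---|---|---|
| 10 points | 0 / 4.9% | 2 / 6.7% | 4 / 12.5% |
| 20 points | 0 / 4.6% | 4 / 12.1% | 8 / 35.9% |
| 30 points | 0 / 4.0% | 6 / 21.4% | 12 / 68.3% |

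The first column shows the condition: with equal agreement there is no bias, and the pooled test is slightly conservative. If response does not differ by centre, the bias is also zero and the error rate is 5.0% whatever the agreement gap.

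**2. What stratification does in the same example.** Weight each centre's difference by n2·n3/(n2+n3). Centre A has 120 agreeing and 80 refusing, and centre B the reverse, so each weight is 120 × 80 / 200 = 48. Both within-centre differences are zero, so the stratified difference is (48 × 0 + 48 × 0) / 96 = 0. Its SE is √(0.24 / 96) = 0.0500, the same as the pooled SE to three significant figures, so precision is not lost here.

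**3. Several centres.** The simulation draws each centre's log-odds of response and of agreement independently, with no effect within centres, in 3,000 runs per setting. It uses 2,000 patients and a lead centre holding 40%. Ranges cover repeat runs.

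| Setting | Pooled test rejects | Centre-stratified CMH rejects |
|---|---|---|
| 5 centres, SD 0.5 for both | 15–16% | 4.4–5.3% |
| 10 centres, SD 0.5 for both | 11–12.5% | 5.0–5.1% |
| 5 or 10 centres, SD 0.3 for both | 6–7% | about 5% |

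Simulation error at a true 5% is √(0.05 × 0.95 / 3,000) = 0.4 points.

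**4. Where the excess disappears.** These are pooled-test rejection rates.

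- Response SD 0.5, agreement SD 0, 2,000 patients: 5.4%.
- Lead centre holding 90% of 2,000 patients: 6.4% at SD 0.5 and 5.0% at SD 0.3.
- 500 patients at SD 0.3: 5.1–5.7%.

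**The case against.** **Allocation may be random.** A.3 does say so. If groups 2 and 3 really were randomised, the share in each would be about equal at every centre and this bias would largely vanish. But groups defined by refusing and agreeing cannot also be random, and the passages must be reconciled. While the definitions stand, the objection does not remove the point.

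**Follow-up may be central.** A.3 says "These patients will be informed to the Department of Infectious Diseases of the Second Affiliated Hospital of Chongqing Medical University for follow-up". If all advice and care sat there, differences by centre in agreement would shrink. This stands as a reason for caution about size. It sits awkwardly with a multi-centre design and needs clarifying.

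**The test list is open.** The count tests end in an open list, and CMH is named. This is true, but nothing assigns CMH to the main index or names its stratum. Nor does every listed method ignore centre: paired tests compare a patient with himself or herself, so stable centre differences in level cancel.

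**A reader might infer that correlation within centres makes the group contrast's standard error too small.** The working does not support that: when only response varies by centre, the pooled test stays near 5%. The mechanism is confounding by centre. A general claim that the confidence intervals are wrong also fails, because the plan lists an interval only among descriptive statistics and gives no method for it.

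**A reader might carry the plan's 16,200 patients into the simulation.** Spread over 10 centres at SD 0.5 this gives rejection of about 39%. But A.3 derives 16,200 from the lead hospital's own screening volume (30% of 54,000), so it is not a multi-centre analysis sample and should not be used this way.

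**Conclusion.** The point holds in conditional form. The plan compares a binary main index between self-selected groups in a multi-centre study by tests that take no account of centre. If both agreement and response differ by centre, the contrast is biased; if either is constant, it is not.

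The size cannot be computed from the documents. Under the assumptions in the first simulation table, the false-positive rate is about 6% to 16% in place of 5%, and it moves towards 5% with smaller samples, smaller centre differences or one dominant centre. The evidence supports a better choice of method at little cost, and does not show that the result will be wrong. Centre is also only one part of the selection problem: patients who agree may differ from those who refuse within the same centre, and that threat is larger.

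**What to change.** In B.2:

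- Test the main index and the other binary between-group comparisons by CMH stratified by centre, and report a centre-stratified risk difference with its 95% CI.
- Include centre as a fixed factor in the between-group models for eGFR, SCr and BMD. Paired within-patient tests can stay as they are.
- Fix in advance a rule for merging very small centres into one stratum.
- State the number of centres and the patients per centre, and reconcile the multi-centre description with follow-up at one department.

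The cost is SAP wording, a few degrees of freedom and the merging rule. CMH is already listed; the stratified risk difference and its interval are additions. Stratifying by centre does not deal with self-selection within centres, which needs its own adjustment for baseline differences between those who refuse and those who agree.

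### Repeated-measures ANOVA is planned without naming its outcome or a missing-data rule for kidney and bone measures; a mixed model using all observed visits would be better

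*Combined protocol and SAP*

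**What the plan says.** All references are to the combined protocol and SAP.

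- **Method.** B.3 Statistical expression, in its item on presenting repeated measurements in tables and charts, states that "F value and P value of an OVA of repeated measurement data are added". It gives no outcome, covariance structure or rule for incomplete patients.
- **Candidate outcome.** A.4 Outcome indexes, secondary index 3, is "Changes of bone and kidney indicators (eGFR, SCr, BMD, etc.) compared with baseline at each follow-up time point". The other listed outcomes (virologic response, normal ALT) are proportions.
- **Missing data.** The rule in B.1 Statistical description begins "Management of missing value in major efficacy indicators data: when a major efficacy data is missing in individual subjects, the method of filling is determined", leaving the method to later judgement. It then adds: "If the case is lost, data from the previous measurement shall be transferred". That sentence names no outcome.
- **Other tests.** B.2 Statistical inference method lists, for continuous data, "The measurement data: T test, paired T test, rank sum test, paired" rank sum test and correlation.
- **Visits.** Virologic response is assessed at week 24 (main index) and "at 12 weeks, 48 weeks and 96 weeks after therapy adjustment" (secondary). No separate schedule is given for kidney and bone measures.
- **Setting.** A.2 describes a "96-week multi-centre prospective real world study".

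**The concern.** Classical repeated-measures ANOVA needs a value at every visit. A patient with one gap is dropped altogether unless the gap is filled. Over 96 weeks of routine care, gaps are to be expected, and patients who miss visits may differ from those who attend them all.

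The plan does not clearly say what happens to a missing eGFR, SCr or BMD value. The filling rule is worded for main efficacy data, which these are not. The lost-case sentence follows under the same heading, so it can be read as covering efficacy only or as covering everything on a lost patient. The first reading leads to deletion in the ANOVA, the second to carrying an earlier value forward.

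At stake is the only comparison over time of kidney and bone measures that the plan offers. Deletion shrinks the sample and may select it. Carry-forward can make a continuing decline look smaller than it is.

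**Working it through.** The documents give no missing rate, dropout rate or visit-completeness figure, so there is no stated figure to reproduce. What follows is illustration under stated assumptions.

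**1. Which outcome the ANOVA fits.** An F value from repeated-measures ANOVA suits a continuous outcome measured several times. Of the outcomes in A.4, only secondary index 3 qualifies. This is an inference; the plan does not make the link.

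**2. Loss of patients if nothing is filled.** Assume complete baseline values, four follow-up visits (weeks 12, 24, 48 and 96, which are stated only for virologic response) and a proportion *m* missing at each visit.

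- Least loss, when the same patients miss every visit: *m*
- Independent missingness: 1 − (1 − *m*)^4
- Greatest loss, when no patient misses two visits: 4*m*

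| *m* per visit | Least | Independent | Greatest |
|---|---|---|---|
| 5% | 5% | 1 − 0.95^4 = 18.5% | 20% |
| 10% | 10% | 1 − 0.90^4 = 34.4% | 40% |
| 20% | 20% | 1 − 0.80^4 = 59.0% | 80% |

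**3. Bias among completers.** A simulation of 400,000 patients in a single group used correlation 0.7 between visits and true mean changes of −0.05, −0.10, −0.20 and −0.40 SD at the four visits. Patients dropped out for good, at about 10% per visit among those remaining. Dropout was either unrelated to the outcome or likelier when the previous value was low (log-odds rising by 1.0 per SD).

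| At week 96 | Truth | Unrelated dropout | Value-dependent dropout |
|---|---|---|---|
| Completers | – | 65.6% | 59.8% |
| Completers' baseline mean | 0 | 0.00 | +0.31 |
| Completers' week-96 mean | −0.40 | −0.40 | −0.12 |
| Completers' change | −0.40 | −0.40 | −0.43 |
| Change with carry-forward | −0.40 | −0.29 | −0.36 |

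With value-dependent dropout, completers are a selected group in level, starting 0.31 SD too high. Their change from baseline is nearly right.

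**4. Carry-forward by hand, unrelated dropout.** Each dropout keeps the last mean change reached:

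−0.40 × 0.9^4 − 0.20 × (0.9^3 × 0.1) − 0.10 × (0.9^2 × 0.1) − 0.05 × (0.9 × 0.1) = −0.2624 − 0.0146 − 0.0081 − 0.0045 = −0.29

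The decline is understated by (0.40 − 0.29)/0.40, about 28%, although the dropout itself is harmless. With value-dependent dropout it is (0.40 − 0.36)/0.40, about 10%.

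**The case against.** The strongest reply is that the ANOVA is only an addition to tables and charts, in a section on presentation. Secondary index 3 compares each time point with baseline, and the paired tests in B.2 do just that. They need only baseline and the visit in question, so a patient who missed week 12 still counts at week 96. This stands: complete-case loss affects the F test and not the paired tests. But paired tests work within a group. The unpaired tests also listed could compare two groups at one visit at a time. None of them gives a group-by-time comparison, which would have to come from the ANOVA.

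Other parts of the reply also stand:

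- The plan never ties the ANOVA to kidney and bone measures, so a reader who infers that those trends will rest on completers goes beyond the text.
- The 34.4% depends on independence. Loss to follow-up tends to cluster within patients, which moves the figure towards the lower end of the range.
- Completer analysis is not biased by default. The simulated bias in change was nil with unrelated dropout, and small and towards more decline otherwise.
- Unequally spaced visits do not in themselves breach sphericity, and corrections exist, so that is a secondary matter.
- No SPSS procedure is named, so a mixed model is not ruled out.

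**Conclusion.** The point holds as a gap in the plan with a cheap and better alternative. The plan adds a repeated-measures ANOVA without naming its outcome, and the one outcome that fits has no clear missing-data rule. Run unfilled and in classical form, the F test would lose 10% to 40% of patients at an assumed 10% missing per visit over four assumed visits. The cost is precision, plus bias if missingness relates to the outcome. If values are carried forward instead, a progressive decline can be understated, by about 10% to 28% in the simulated setting.

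The documents do not support the firmer reading that the kidney and bone results will be biased or will come from a selected subset. That would need a missing rate, a link between missingness and outcome, and a definite choice between deletion and carry-forward; the documents give none of these. Deletion and carry-forward are alternatives for the same lost patient, so their effects should not be added together. The simulation has no treatment groups and does not measure bias in a group difference. The main index, a proportion at week 24, is not touched.

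**What to change.** In B.2 and B.3, name eGFR, SCr and BMD as the outcomes for repeated-measures analysis, state the visits at which each is measured, and replace the ANOVA for them by a linear mixed model for repeated measures (MIXED in the named SPSS software):

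- Fixed effects: group, visit, group-by-visit, baseline value and centre.
- Unstructured covariance across visits; with four visits this is 4 × 5/2 = 10 parameters.
- All observed values used, none carried forward. Say in B.1 that the lost-case sentence does not apply to these outcomes.
- Report group differences in change at each visit with 95% confidence intervals, and the number observed per visit and group.

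A.3 speaks of random division into three groups but also defines groups 2 and 3 by refusing or agreeing to change regimen. Unless those statements are reconciled, describe the contrast between these groups as non-randomised. The model does not remove self-selection.

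The cost is SAP wording and slightly more analysis work, with no new data. The downside is reliance on values being missing at random given the observed data, which should be stated when the results are reported.

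### Kidney and bone outcomes have no clear missing-data rule, and the planned ANOVA, if run as SPSS GLM Repeated Measures, drops any patient with one missed visit

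*Combined protocol and SAP*

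**What the plan says.** - Section B.3 (Statistical expression) plans tables and charts for repeated measurements and states "F value and P value of an OVA of repeated measurement data are added". I read the garbled word as ANOVA. No variables, model or treatment of incomplete cases are given.
- Section B.4 states only "SPSS22.0 software will be used for analysis".
- Section A.4, secondary index 3, is "Changes of bone and kidney indicators (eGFR, SCr, BMD, etc.) compared with baseline at each follow-up time point". The virologic and ALT indexes are proportions, so this is the only continuous repeated outcome listed.
- Section B.1 opens its missing-data rule with "Management of missing value in major efficacy indicators data: when a major efficacy data is missing in individual subjects" and leaves the filling method to later judgement. The next sentence reads "If the case is lost, data from the previous measurement shall be transferred".
- Section B.2 lists the tests for continuous data, beginning "The measurement data: T test, paired T test, rank sum test, paired". ANOVA is not in that list.
- Section A.2 describes a "96-week multi-centre prospective real world study". Section A.4 names week 24 for the main virologic index and, for the secondary one, "at 12 weeks, 48 weeks and 96 weeks after therapy adjustment". Kidney and bone measurements have no visit schedule of their own, and no drop-out rate is assumed anywhere.

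**The concern.** The usual SPSS procedure for a repeated-measures ANOVA, GLM Repeated Measures, needs a value at every visit and deletes any patient with a gap. Over 96 weeks of routine care gaps are foreseeable, and the plan itself expects lost cases. No rule clearly covers a missed eGFR, SCr or BMD. The question is therefore who is analysed, which a sphericity correction would not change. A rule for missing HBV DNA would not settle it either.

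These are the study's only listed kidney and bone outcomes, in a study built around changing the antiviral regimen. If patients whose kidney function or bone density falls are more likely to leave, those who remain are a healthier group and the reported decline may be too small.

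**Working it through.** The plan gives no missingness, SD or expected change for these outcomes, so there is no figure of its own to reproduce. Every input below is an assumption except the visit weeks, which are borrowed from the virologic indexes (12, 24, 48 and 96).

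**Step 1: patients kept.** Let baseline be complete and each follow-up visit be missing independently with probability p. The ANOVA by GLM Repeated Measures keeps (1-p)^4. A paired comparison of baseline with week 96 keeps 1-p.

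| p | ANOVA, four follow-ups | Paired, week 96 |
|---|---|---|
| 5% | 0.95^4 = 81% | 95% |
| 10% | 0.90^4 = 66% | 90% |
| 20% | 0.80^4 = 41% | 80% |

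If BMD were measured at only two follow-ups, the ANOVA would keep (1-p)^2 = 90%, 81% or 64%.

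**Step 2: bias of the planned methods.** Simulation of 200,000 patients at weeks 0, 12, 24, 48 and 96. Inputs: true mean change at week 96 of -5.0 units, between-patient SD of change 6, measurement SD 5, 20% drop-out by week 96, and 10% intermittent missingness at weeks 12, 24 and 48. Complete cases are 0.9^3 x 0.8 = 58%; the paired comparison keeps 80%. Estimated week-96 change:

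| Drop-out | Complete cases | Paired, week 96 | Carry-forward |
|---|---|---|---|
| Unrelated to decline | -5.0 | -5.0 | -4.2 |
| More likely with worse decline | -3.9 to -4.6 | -3.9 to -4.6 | -3.4 to -4.6 |
| More likely with milder decline | -5.8 to -6.1 | -5.8 to -6.1 | -3.9 to -4.9 |

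In the second row the complete-case result is short by (5.0 - 4.6)/5.0 = 8% to (5.0 - 3.9)/5.0 = 22%. At 30% drop-out with the strongest link to decline, complete cases gave -3.2, paired -3.3 and carry-forward -2.7.

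**Step 3: does a likelihood model help?** A second simulation used a true week-96 change of -6.0, slope SD 6, error SD 5 and intermittent misses of 5-10%. Drop-out was 3-5% per visit, rising to 25-40% after a fall of more than 8.

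- Complete cases: 43-63% of patients kept, change -4.5 to -5.1.
- Paired, week 96: -4.5 to -5.2.
- Carry-forward: -4.8 to -5.3.
- Maximum likelihood on all observed values, equivalent to a mixed model with unstructured covariance: about -5.9 in one run and -6.0 to -6.1 in another.

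With the same drop-out rule in both groups, the complete-case group contrast moved less: about -3.8 against a true -4.0. With purely random missingness at the mildest rates, complete cases were unbiased but only 0.97^4 x 0.95^4 = 72% of patients remained, a loss of 28%.

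**The case against.** A reader might infer that the 96-week kidney and bone results will describe completers only, and that the reported decline will be too small. The documents do not support either as a certainty, for five reasons.

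1. The paired tests in B.2 fit secondary index 3 directly and use everyone with a baseline value and that visit. ANOVA appears only in the reporting section, as something added, and is not tied to eGFR, SCr or BMD. This stands: the loss of patients in Step 1 applies to the F test alone. It does not remove the bias, because the paired results were nearly identical to the complete-case results in Step 2.
2. The carry-forward sentence in B.1 follows the efficacy heading but is not itself limited to efficacy. On the wider reading, lost patients stay in with carried values. The ambiguity stands. Even so, the sentence speaks of lost cases, not of one missed measurement in a patient who continues, and carry-forward understated the change even when drop-out was unrelated to decline.
3. SPSS MIXED also produces F and P values and does not delete incomplete patients. The procedure is not named, so the point must be conditional. But the plan says ANOVA and mentions no mixed model, covariance structure or use of all observed values.
4. The direction of bias depends on why patients leave, and the documents say nothing on this. This stands in full: the bias can be nil or reversed.
5. The four-visit schedule is borrowed from the virologic indexes. This also stands; fewer BMD visits would mean fewer exclusions.

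**Conclusion.** The point holds in conditional form. The plan has no explicit missing-data rule for its kidney and bone outcomes. The method it names for repeated measurements, run as GLM Repeated Measures without imputation, would drop every patient with one missed visit from that test. With four follow-ups and 5-20% missing per visit, that leaves 81% down to 41% of patients, against 95% down to 80% for a paired week-96 comparison.

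Understated decline is a possibility, not a finding. It needs patients with worse decline to leave more often. With 20% drop-out in the first simulation, the complete-case and paired estimates then fell short by 8% to 22%. Under random missingness those two methods lose precision only, while carry-forward can still understate the decline. If patients with milder decline leave, complete-case and paired analyses overstate it. Between-group contrasts may be less affected when drop-out works alike in the groups. The weakness therefore lies in the ANOVA, the paired tests and carry-forward together, and mending the ANOVA alone would leave most of it in place. The outcome is secondary, and a better analysis is available in the same software, so the change is worth making.

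**What to change.** For change in eGFR, SCr and BMD, replace the repeated-measures ANOVA in B.3 with a linear mixed model (MIXED in SPSS 22.0). Let it also replace the paired and two-sample tests of B.2 as the main inference for secondary index 3.

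- Fit the model to all observed values, without carry-forward and without restricting to patients with complete visits.
- Include group, visit as a category, group-by-visit and the baseline value, with unstructured within-patient covariance.
- Report the estimated change and the group difference with 95% CI, and the number of patients observed, at each visit.
- State in B.1 that the filling and carry-forward rules do not apply to these outcomes.
- State the limit: the model corrects only for drop-out explained by observed values. It does not cure loss driven by decline that was never measured.

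The cost is SAP wording and slightly more analysis work. No new software, data or patients are needed.
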